### 7.2. Data Analysis Plan

The sample, both the baseline characteristics and the outcomes, will be explored and described using graphical techniques and summary statistics (means, medians, proportions and measures of variability) as appropriate. The initial description will consider the sample as a whole as well as by treatment arm.

The primary outcome variable will be the global rank score, as used previously in several similar randomized controlled trials to facilitate evaluation of composite outcomes of binary and continuous findings accounting for censorship for death. The predictor of interest for all outcomes will be randomized intervention (fenofibrate vs. control), with analyses based upon the total number of randomized participants. Initial descriptive estimates of all measures will be generated for study participants by treatment group. Statistics will include estimates of central tendency, measures of variability, and derived moments of skewness and kurtosis. Analyses of distributional properties will be performed to determine if variance stabilizing or normalizing transformations should be applied. Outliers will be assessed via visual inspection of distributions and checked for accuracy. Additionally, the intervention groups will be compared using Fisher's Exact tests.

The primary and secondary outcomes will be analyzed using a two-sided Wilcoxon rank sum test. Estimation, and 95% confidence intervals, of the differences between arms will be based on the Hodges-Lehman median difference as well as the Mann-Whitney Parameter, the probability that a subject from the fenofibrate arm has a score greater or equal to that of a subject for the control. This will be followed by a more comprehensive linear regression analysis allowing for assessments of the treatment effect on each continuous outcome of interest while controlling for effects of covariates including age, sex, inpatient vs. outpatient status at enrollment,  $\text{FiO}_2/\text{SpO}_2$  at the time of enrollment, ethnicity, body mass index, altitude above sea level and history of diabetes at baseline.

For non-normal distributed continuous outcomes, we will utilize non-parametric methods or consider distribution-stabilizing transformations. Levine's tests will be used to assess homogeneity of variance. The models will include data from dropouts. Model assumptions will be examined (eg, QQ plots to assess normally distributed residuals for valid Wald tests).

All-cause death will be evaluated using Cox proportional hazards models. The proportional hazards assumption will be assessed via weighted versions of Kaplan-Meier curves, using log-log plots and graphical displays based on the Schoenfeld and scaled Schoenfeld residuals, and violations of the proportional hazards assumption will be addressed with a time-interaction term.

We will make every possible effort to minimize missing data and ensure final assessments for participants opting to discontinue study participation. Missing data, however, is an inevitable problem in a longitudinal study. The mechanism for missingness-missing completely at random (MCAR), missing at random (MAR), nonignorable or not missing at random (NMAR)-will be evaluated prior to implementing methodology intended to minimize bias from missing data. We anticipate that <5% of randomized subjects will have missing data in the components required to compute the study outcomes. Imputation procedures will be applied as needed for missing data, and the primary analyses will use the imputed data.

The intent-to-treat principle of including all randomized participants in the outcome models will be followed. Analytic methods described above will take advantage of all available data. Sensitivity analyses will be performed including only participants with laboratory confirmation of COVID-19 and using an 'as-treated' analysis. The 'as-treated' analysis will take into account subjects in the control arm who begin fenofibrate as part of their clinical care, and those in the fenofibrate arm who stop using fenofibrate for any reason. We will also perform sensitivity analyses in which the  $\text{FiO}_2/\text{SpO}_2$  ratio will be theoretically normalized for altitude above sea level (atmospheric pressure).

Sequential monitoring and early stopping: Incidence rates of outcomes will be monitored throughout the trial and used for an interim analysis of efficacy and futility at 50% of enrollment. Group sequential methods for event rates will be used to control the Type I error to be 0.05 across repeated analyses. Critical values for interim testing will be defined based on an O'Brien-Fleming type bound (alpha 0.0052). With this approach, the interim test is conservative and the reduction in the overall power of the trial caused by interim testing is small. If needed, conditional power calculations will be used to assess the futility of continuation in the presence of a negative treatment effect. The DSMB will review data on adverse events and other safety issues to make an overall recommendation concerning the safety of continuing the trial.

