### 3. ENDPOINTS

The **primary endpoint** of the trial will be a global rank score that ranks patient outcomes according to 5 factors: (1) time to death (ranked from shortest to longest, up to 30 days post-randomization), (2) the number of days supported by mechanical ventilation (invasive or non-invasive) or extracorporeal membrane oxygenation (until hospital discharge, up to 30 days post-randomization, ranked from longest to shortest); (3) The inspired concentration of oxygen/percent oxygen saturation ( $\text{FiO}_2/\text{SpO}_2$ ) ratio area under the curve (until hospital discharge, up to 30 days post-randomization, ranked from highest to lowest); (4) For participants enrolled as outpatients who are subsequently hospitalized, the number of days out of the hospital during the 30 day-period following randomization (ranked from lowest to highest); (5) For participants enrolled as outpatients who don't get hospitalized during the 30-day observation period, the modified Borg dyspnea scale (mean value of assessments at ~5, ~10 and ~15 days). Patients who are enrolled as inpatients but discharged within 24 hours of receiving the first dose of the study medication will be ranked similarly to outpatients.

The global rank score has several advantages compared to binary outcomes (e.g., all-cause death) or time-to-event outcomes (e.g., time to death). It incorporates information about each of the highest-priority events in COVID-19, but allows these events to be prioritized within a single endpoint. For instance, the principal outcome of interest is death, but even if there is no difference in rate of death, we would still be interested in a shorter duration of invasive respiratory support, a shorter duration of hospital admission with better oxygenation parameters, and so on. This maximizes study power and minimizes the number of participants that need to be enrolled in order to detect clinically-meaningful differences.

**Figure 2** demonstrates how participants will be ranked hierarchically according to their clinical course. All primary analyses will be performed on an intent-to-treat basis.

**Secondary endpoints** will include:

- (1) Number of days alive, out of the intensive care unit, free of mechanical ventilation (invasive and non-invasive), extracorporeal membrane oxygenation (ECMO) or maximal available respiratory support in the 30 days following randomization.

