## 7. STATISTICAL CONSIDERATIONS

### 7.1. Power calculations

We will enroll 700 participants. Participants will be randomized to one of 2 interventions (fenofibrate plus usual care vs. placebo plus usual care). Assuming feasible distributions of participants across each of the five hierarchies from the available published evidence, we performed 10,000 simulations of rank distributions of 700 participants, and determined that there will be 80% power at an alpha of 0.0492 (allowing for one interim analysis at 50% of enrollment with an alpha of 0.0054) to observe an 11% difference in median rank scores between the treatment arms. Power calculations were performed using python and PASS16.

Enrollment of 700 participants will increase our power for secondary outcomes. For the secondary outcome of number of days alive, out of the intensive care unit, free of mechanical ventilation (invasive and non-invasive), extracorporeal membrane oxygenation (ECMO) or maximal available respiratory support in the 30 days following randomization, assuming a standard deviation of 7 (the SD from the REPLACE COVID trial for this outcome), a sample size of 700 would have 90% power to estimate a 1.7 day mean difference between treatment arms. Assuming that the SD may be higher in the current study with the inclusion of outpatients, we would have a sufficient power to estimate a 3.4 day mean difference between treatment arms with a SD of 14.

For the secondary outcome of the WHO ordinal scale, based on the ordinal scale distributions from the Remdesivir trial, we would have 90% power to observe an OR of 1.5 for clinical improvement in the ordinal scale. Given the expected lower severity of illness in our participants, with an adjusted reasonable distribution towards the lower end of the scale, we would have 90% power to observe an OR of 1.7.

For the exploratory outcome of all-cause death, assuming a death rate of 14% (observed in REPLACE COVID), we would have sufficient statistical power to detect a HR of 1.4. Considering the mixed inclusion of inpatients and outpatients, if the death rate is 5%, we would have sufficient statistical power to detect a HR of 1.7.

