### Descriptive Statistics (Intention to treat cohort)

Analyses will be for the overall cohort, stratified by arm and stratified by in/out patient status at randomization. The outcomes and baseline characteristics of the subjects will be described using proportions for categorical variables and means/medians as well as standard deviations (SD) and interquartile range (IQR) for continuous variables.

**Primary Analysis:** This analysis will use a two-sided van Elteren test, the stratified version of the Wilcoxon rank sum test. For each stratum, estimation, and 95% confidence intervals of differences between arms will use both the Hodges-Lehman median difference and the Mann-Whitney Parameter, the probability that a subject from the treatment arm has a score greater or equal to that of a subject for the control. In addition to the primary outcome, the Wilcoxon test will be used to test hypotheses involving the continuous secondary and exploratory outcomes.

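### If most participants reach the 30-day ceiling, the Hodges-Lehmann difference for the first secondary endpoint is 0 (0 to 0) even with a real benefit; the primary stratified test also lacks a stated overall estimate

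*Protocol*

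**What the plan says.** Protocol section 3 defines the first secondary endpoint as "Number of days alive, out of the intensive care unit, free of mechanical ventilation", ECMO or "maximal available respiratory support in the 30 days following randomization". It is a count from 0 to 30, and a survivor who never needs ICU care or any of the listed support scores 30.

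Protocol section 7.1 powers this endpoint on a difference in means, "assuming a standard deviation of 7 (the SD from the REPLACE COVID trial for this outcome"), and concludes that "a sample size of 700 would have 90% power to estimate a 1.7 day mean difference between treatment arms".

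Protocol section 7.2 then says "The primary and secondary outcomes will be analyzed using a two-sided Wilcoxon rank sum test" and "Estimation, and 95% confidence intervals, of the differences between arms will be based on the Hodges-Lehman median difference as well as the Mann-Whitney Parameter". It defines the second of these estimators as "the probability that a subject from the fenofibrate arm has a score greater or equal to that of a subject for the control". A covariate-adjusted linear regression of each continuous outcome follows.

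The SAP (Analysis, Primary Analysis paragraph) changes the primary test to a van Elteren test and says: "For each stratum, estimation, and 95% confidence intervals of differences between arms will use both the Hodges-Lehman median difference and the Mann-Whitney Parameter". For the continuous secondary outcomes it names the Wilcoxon test and does not mention the Hodges-Lehmann difference again. Its Regression models paragraph keeps the adjusted linear regression.

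**The concern.** The Hodges-Lehmann estimate is the median of all pairwise differences between arms. When a large share of both arms has the same value, so many pairs tie that the median is exactly 0. With enough ties, both confidence limits are 0 as well. A day count with a hard ceiling at 30, in a trial that excludes intubated patients and enrols outpatients, is a natural place for this.

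A significant Wilcoxon test could then be reported beside a difference of 0 days (95% CI 0 to 0). That says nothing about the mean difference on which the endpoint was powered.

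The primary endpoint has a related gap. A stratified test gives one p-value across strata, but the SAP pairs it with separate stratum estimates and states no overall effect to go with that p-value.

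**Working it through.** **Inputs from the documents.** 700 participants, 1:1, so 350 per arm (Protocol 2.3 and 2.5). SD 7 or 14, mean difference 1.7 or 3.4 days, deaths 14% or 5% (7.1). Intubated patients excluded (2.3); outpatients enrolled (2.4 and 2.10); lower severity expected (7.1). **Assumed:** the share at 30 days, varied below, and values below the ceiling uniform on 0 to 29.

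**1. The plan's own figure.** Detectable difference = (1.960 + 1.2816) × 7 × √(2/350) = 1.715 days. At exactly 1.7 days, two-sided alpha 0.05, power is 89.5%. With SD 14 the difference doubles to 3.43. The stated 1.7 and 3.4 reproduce.

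**2. When the estimate is 0.** Let D be treated minus control. P(D ≤ 0) is at least the control share at 30, and P(D ≥ 0) is at least the treated share at 30. If both shares exceed 50%, the median of D is 0.

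**3. When both limits are 0.** The usual 95% limits are order statistics of the pairwise differences, at 50% ± 1.96 × √((N+1)/(12nm)). With N = 700 and n = m = 350 this is 1.96 × √(701/1,470,000) = 1.96 × 0.0218 = 4.28 points. The limits are therefore the 45.7th and 54.3rd percentiles. If more than about 54.3% of each arm scores 30, both are 0. A tie correction narrows the limits, which lowers the threshold slightly.

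**4. Is such a share plausible?** At 5% deaths, the share at 30 falls to 50% only if 100 − 5 − 50 = 45% of participants survive but spend time in ICU or on the listed support. At 14% deaths the figure is 100 − 14 − 50 = 36%. The SD alone does not settle it. An SD of 7 implies 82% at 30 if the rest are uniform and 94% if the rest are at 0, but clipped-normal shapes with about the same SD allow 6% to 66%.

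**5. Simulation, 350 per arm, 400 trials per row.** The mean is 30p + 14.5(1 − p), so the true difference is 15.5 × (treated share − control share).

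| At 30 days, control → treated | True difference (days) | Estimate = 0 | CI 0 to 0 |
|---|---|---|---|
| 35% → 46% | 1.7 | 89% | 29% |
| 40% → 51% | 1.7 | 98.5% | 68% |
| 45% → 56% | 1.7 | 100% | 91% |
| 50% → 61% | 1.7 | 100% | 99% |
| 80% → 91% | 1.7 | 100% | 100% |
| 60% → 90% | 4.65 | at least 99.8% | 99.8% |
| 50% → 90% | 6.2 | 83% | 26% |
| 55% → 35% (harm) | −3.1 | 49% | 4% |

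The Wilcoxon test rejected in 99% of trials at 80% → 91%, and in about 90% at 60% → 72%. A clipped normal with SD 6.9 and 6% at the ceiling gives 2 (1 to 3) for a 1.7-day effect, so a low ceiling share removes the problem.

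**6. The Mann-Whitney wording.** With 80% at 30 in both arms and no effect, P(X > Y) = 0.8 × 0.2 + 0.2² × 29/60 = 0.179 and P(X = Y) = 0.8² + 0.2²/30 = 0.641. Counting ties in full gives a no-effect value of 0.82. Splitting them gives 0.179 + 0.641/2 = 0.50. At 80% → 91%, the tie-split value is 0.555.

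**7. Overall against stratum precision for the primary.** Ignoring ties, the CI half-width is 1.96 × √((N+1)/(12nm)). For 700 participants it is 0.043. For a stratum of 350 (175 per arm) it is 1.96 × 0.0309 = 0.061. Two equal strata are an illustration only, because the SAP does not define the van Elteren strata.

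**The case against.** Several points against this are sound.

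- No document gives the share at 30 days. A reader might infer that the estimate must be 0 regardless of the drug's effect. The documents do not support that: the share is an assumption, and the last two rows of the table and the low-ceiling example show non-zero results.
- A reader might infer that a 0 to 0 interval is an error. It is not. In these scenarios the population median pairwise difference is 0, and the interval covers it. It simply carries no information about mean days.
- The SAP names the Hodges-Lehmann difference under the primary analysis only. Its use for this secondary endpoint rests on Protocol 7.2, which the SAP says it follows.
- A benefit would not be wholly hidden. The Mann-Whitney parameter and the adjusted regression are both planned, and the SAP describes outcomes with means and medians by arm.
- The SAP does not exclude an overall primary estimate, and Protocol 7.2 describes an unstratified one.
- A reader might extend the argument to outpatients whose mean Borg score is 0. No document gives that share, so nothing is claimed here.

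These points limit the claim without removing it. The regression is a follow-on and not the estimate paired with the test, and for non-normal outcomes Protocol 7.2 allows non-parametric methods or a transformation instead. The Mann-Whitney parameter as worded counts ties in full, so heavy ties make it hard to read too. An unstratified estimate does not match a stratified test.

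**Conclusion.** The point holds in conditional form. If more than about 54% of each arm scores 30, the Hodges-Lehmann result for the first secondary endpoint is 0 (0 to 0) at 350 per arm, even when the 1.7-day mean difference is real and the Wilcoxon test rejects. The case mix makes that share plausible, but the documents do not establish it. Below about 50% the collapse becomes less certain: at a 35% control share it occurs in 29% of trials. With large harm, or within a sicker inpatient group, the result may be non-zero.

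The percentages in the table rest on the uniform shape below the ceiling; the 50% and 54% thresholds do not. Software that treats ties differently may print slightly different limits.

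The missing overall primary estimate does not depend on the ceiling. Its illustrated size, 0.043 against 0.061, assumes two equal strata. Both matters concern what is reported and leave the validity of the tests untouched.

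**What to change.** (a) For the first secondary endpoint, replace the Hodges-Lehmann difference with the difference in mean days and a bootstrap 95% CI, which is the scale used in Protocol 7.1. Report beside it the Mann-Whitney parameter defined as P(X > Y) + 0.5 × P(X = Y), so that no effect is 0.50. State the share of participants expected at 30 days.

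(b) For the primary endpoint, name the van Elteren strata. Report one stratum-weighted, tie-split Mann-Whitney estimate with a 95% CI, using the same weights as the test, as the headline effect. Keep the stratum values as description.

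The cost is a few lines of SAP text and minor programming. No extra data are needed, and nothing changes for participants.

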## **2.7. Participant withdrawal / Early termination**

Participants may voluntarily withdraw from the study at any time and for any reason. The reason for study discontinuation will be recorded on the source documents and in all such participants, we will document: (1) vital signs (inpatients only); (2) compliance with the treatment; (3) adverse effects. (4) specific reason for withdrawal if possible; (5) functional status and symptoms (including the dyspnea Borg scale).

The study medication will be discontinued if any of the following occur at any time: (1) acute kidney injury with eGFR<30 ml/m^2/min; (2) Suspected or confirmed rhabdomyolysis; (3) Red or brown urine, which may indicate myoglobinuria, unless considered by the investigator to be clearly not due to rhabdomyolysis (for instance, in the presence of normal circulating creatine kinase); (4) Liver failure or increased AST or ALT to >3 times the upper limit of normal. In cases in which the medication is discontinued, data collection will continue normally as per the usual study protocol.

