## ANALYSIS

**Intention to Treat Principle** Unless otherwise specified, all analyses are conducted on an 'as-randomized' basis, irrespective of adherence to treatment. This analysis follows the intention to treat principle pre-specified in the protocol.

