### Sensitivity Analyses

1. **Per-Protocol and As-Treated Analysis.** The extent of non-adherence to protocol will be described by arm. Cumulative event plots will be used to compare non-adherence to protocol (as a binary event) by arm. If there is a substantial difference in non-adherence

across treatment arms, we will adjust for non-adherence in the secondary analyses of the primary endpoint

2. The  $\text{FiO}_2/\text{SpO}_2$  ratio will be normalized for altitude above sea level (atmospheric pressure) using standard equations.
3. **Incomplete Data** While missing data is an inevitable problem in longitudinal studies, we will make every possible effort to ensure final assessments for all participants, including those opting to discontinue study participation. Possible mechanisms for missingness-missing completely at random (MCAR), missing at random (MAR), nonignorable or not missing at random (NMAR)-will be evaluated prior to implementing methodology intended to minimize bias from missing data. We anticipate that <5% of randomized subjects will have missing data in the components required to compute the study outcomes. Imputation is not commonly used for rank-based statistical methods such as the van Elteren or Wilcoxon Rank-sum test. If the missingness rate exceeds 5%, we will carry out a sensitivity analysis of the primary outcome using linear regression with multiple imputation. The primary analysis will be a complete case analysis.

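### The planned as-treated analysis groups by post-randomization stopping, so a null drug can look effective if stopping tracks worse prognosis

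*Protocol*

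**What the plan says.** Protocol section 7.2 announces the analysis: "Sensitivity analyses will be performed including only participants with laboratory confirmation of COVID-19 and using an 'as-treated' analysis". It then names two groups. The first is "subjects in the control arm who begin fenofibrate as part of their clinical care"; the second is "those in the fenofibrate arm who stop using fenofibrate for any reason". The operation applied to them is left open: "The 'as-treated' analysis will take into account subjects in the control arm" and the active-arm stoppers, with no statement that anyone is moved, excluded or censored. No minimum exposure or timing is set, and placebo participants who stop are not mentioned.

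The SAP, under Sensitivity Analyses item 1, keeps the heading "Per-Protocol and As-Treated Analysis". Beneath it, "The extent of non-adherence to protocol will be described by arm", cumulative event plots compare non-adherence between arms, and secondary analyses of the primary endpoint adjust for non-adherence if it differs substantially between arms. Non-adherence is not defined, no threshold is given for a substantial difference, and no adjustment model or as-treated grouping rule is stated.

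Protocol section 2.7 gives the stopping rules: "The study medication will be discontinued if any of the following occur at any time", followed by acute kidney injury, suspected or confirmed rhabdomyolysis, discoloured urine suggesting it, and liver failure or raised transaminases. These apply to blinded medication, so to both arms, and outcome data are still collected after a stop. Section 4.3 lists worsening renal and liver function among the expected events of COVID-19.

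The main analyses are protected. Unless otherwise specified, the SAP states, "all analyses are conducted on an 'as-randomized' basis, irrespective of adherence to treatment".

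**The concern.** Stopping happens after randomization, so groups formed by it are no longer comparable. Suppose active-arm participants who stop have worse outcomes than average. Grouping by treatment received then removes poor ranks from the fenofibrate group and adds them to control, while placebo participants who stop for the same reasons stay in control. The comparison shifts towards fenofibrate even when the drug does nothing and both arms stop equally often. Dropping active-arm stoppers without doing the same for placebo produces a smaller shift in the same direction.

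The SAP's adjustment does not solve this. It conditions on a post-randomization variable, and it is not called for when the arms stop at similar rates, which is a setting in which the regrouping bias already arises.

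At stake is the reading of a robustness check. A positive as-treated result beside a neutral intention-to-treat result could be taken as benefit among those who took the drug, when the plan gives no means of telling it from selection.

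**Working it through.** The documents give no stopping rate, bias or error rate for this analysis, so there is no figure of theirs to reproduce.

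**Inputs from the documents.** 700 participants and 80% power at alpha 0.0492 (protocol 7.1); 1:1 allocation, hence 350 per arm (2.5); two-sided Wilcoxon test (7.2; the SAP uses its stratified form).

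**Assumptions.** No drug effect. The same stopping proportion *s* in both arms, 5% or 10%. A participant stops when a latent variable, correlated *rho* with worse prognosis, exceeds a cut-off. Higher rank means better outcome. Test at 0.05, unstratified.

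**Formulas.** Let *m* be the mean outcome percentile of stoppers (0.50 if stopping is unrelated to prognosis).

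- Regrouped with control: the fenofibrate mean percentile is (0.5 − sm)/(1 − s) and the control mean is (0.5 + sm)/(1 + s). The difference, which is the Mann-Whitney parameter minus 0.5, is s(1 − 2m)/(1 − s²).
- Dropped from the active arm only: the difference is s(0.5 − m)/(1 − s).
- Null standard error: √[(n₁ + n₂ + 1)/(12 n₁n₂)].

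**Worked case, s = 0.10, rho = 0.6.** This gives m = 0.21.

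- Difference after regrouping: 0.10 × 0.58/0.99 = 0.0586, or 0.0586 × 700 = 41 ranks.
- Groups are 315 and 385; standard error = √[701/(12 × 315 × 385)] = 0.02195.
- z = 0.0586/0.02195 = 2.67, so the chance of rejection is about Φ(2.67 − 1.96) = 0.76. Simulation (3,000 replicates) gave 0.774.

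For scale, the same approximation with 350 per arm puts the difference detectable with 80% power at (1.967 + 0.842) × 0.02184 = 0.0613, or about 43 ranks. This is not the plan's own power model, whose tier distributions are not given.

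**Simulated rejection rates under a null drug, equal stopping in both arms**

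| Stopping | rho | m | Regrouped with control | Dropped from active only |
|---|---|---|---|---|
| 5% | 0 | 0.50 | 0.053 | 0.054 |
| 5% | 0.3 | 0.33 | 0.112 | 0.065 |
| 5% | 0.6 | 0.17 | 0.318 | 0.118 |
| 10% | 0 | 0.50 | 0.051 | 0.054 |
| 10% | 0.3 | 0.35 | 0.269 | 0.109 |
| 10% | 0.6 | 0.21 | 0.774 | 0.306 |

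After regrouping with rho above zero, nearly all rejections favour fenofibrate. The as-randomized test stayed at 0.046-0.057 throughout.

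**Outside that range.** At 2% stopping, regrouping gives 0.059 (rho 0.3) to 0.093 (rho 0.6). If those who feel better stop (10%, rho −0.6), regrouping rejects 0.767 of the time, always favouring placebo.

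**Symmetric exclusion.** Dropping stoppers from both arms holds the error near 0.05 when stopping is the same in each arm. With 15% active and 5% placebo stopping (rho 0.6) it rejects 0.242 of the time.

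**The case against.** The strongest reply has four parts.

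First, the protocol never says that stoppers move to control. That is correct, and a reader who infers a written reclassification rule goes beyond the text. Regrouping is the ordinary meaning of the label, and pairing control starters with active stoppers fits it, but it remains an inference. The milder reading, exclusion from the active arm only, still inflates the error.

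Second, the SAP describes non-adherence in both arms and speaks of adjustment, not recoding. This also stands. Yet the SAP says that it follows the protocol's analysis plan with more detail, keeps the as-treated heading and supplies no grouping, so the protocol sentence remains the only account of who is affected.

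Third, stoppers need not be the sickest. Section 8.2 says fenofibrate itself can raise transaminases and creatinine; section 2.8 adds stops for co-medication; the United States part of Appendix 3 has intubated patients continue by nasogastric tube; and stopping for any reason includes stopping on recovery. It would therefore be wrong to infer that the plan removes the sickest participants or favours fenofibrate by construction. The overlap of renal and liver triggers with expected COVID-19 events makes a link with prognosis plausible, not established.

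Fourth, the missing placebo rule is not itself the error: in a comparison by drug received, a placebo stopper is already unexposed, and symmetric exclusion can also fail. This is right, and it is why the fix is a different estimator.

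**Conclusion.** The concern holds conditionally. As planned, the as-treated analysis cannot test the robustness of the intention-to-treat result, because the size and direction of its bias depend on a stopping mechanism that neither document specifies. If stopping tracks worse prognosis, the false-positive rate is about 11-77% under regrouping and about 6.5-31% under one-sided exclusion. Those ranges rest on assumed stopping of 5-10% in both arms and an assumed correlation of 0.3-0.6. With no such link there is no bias; with the opposite link it favours placebo.

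The documents do not support reading this as a threat to the trial's main conclusion. The primary analysis is as randomized, and neither document bases an efficacy claim on the as-treated result.

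**What to change.** 1. Reconcile protocol section 7.2 with SAP Sensitivity Analyses item 1, and state what is done with control starters and active-arm stoppers.
2. Replace both the as-treated contrast and the adjustment for observed non-adherence with a complier-average effect that uses randomized arm as the instrument. Its numerator is the as-randomized difference, so a null drug keeps close to the nominal error rate (4-6% in simulation). Define exposure for partial courses and acknowledge the exclusion restriction: someone who stops on day 9 of 10 has had most of the treatment, so counting that person as unexposed strains the assumption.
3. If a per-protocol set is kept, define non-adherence identically for fenofibrate and placebo capsules, and weight for baseline and available follow-up predictors of stopping. Daily data exist only for inpatients; outpatients are called at about days 5, 10, 15 and 30. Symmetric exclusion alone is not enough.
4. Label the result supportive only.

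The cost is SAP wording, some programming, an added assumption and a wider interval. With 10% active-arm stopping and no control starters, the as-randomized difference and its standard error are both divided by 0.90 (denominator treated as known), which widens the interval by 1/0.90 − 1, about 11%. No new data are needed, provided that study-drug stops and open-label starts are recorded.
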